6.4. Screen Failures

Screen failures are defined as participants who consent to participate in the clinical study but are not subsequently randomised/included. A minimal set of screen failure information is required to ensure transparent reporting of screen failure participants to meet the Consolidated Standards of Reporting Trials (CONSORT) publishing requirements and to respond to queries from regulatory authorities: date of ICF signature by participant, demographics and reason for screen failure will be entered in the eCRF.

Individuals who do not meet the criteria for participation in a given panel (screen failure) may be rescreened for a consecutive panel. Reserve participants may be rescreened (if outside of the protocol window) for a consecutive panel. Rescreened participants will be assigned a new screening number. For the new screening visit, the participant must undergo all screening evaluations planned in the protocol.

7. IMP

7.1. Investigational Medicinal Products Administered

Table 3 provides an overall summary of the investigational medicinal product (IMPs) administered during the study, further information is provided in the Investigator's Brochure [1] and in the IMPD [2].

Table 3: IMPs

Study Treatment Name:	Ir-CPI	Placebo
Active ingredients	Ixodes ricinus -Contact Phase Inhibitor as a non-glycosylated recombinant protein produced in the yeast Pichia Pastoris	NA
Excipients	Phosphate Buffered Saline (PBS)	NA
Dosage formulation:	10 mL vials: 25 mg/mL non-glycosylated recombinant protein produced in the yeast Pichia Pastoris , in 5 mL extractable PBS solution. To be stored at $-20^{\circ}\text{C} \pm 5^{\circ}\text{C}$.	NaCl 0.9% for IV infusion
Unit dose strength(s)/Dosage level(s):	Part I: 1.5 mg/kg, 4.5 mg/kg, 9 mg/kg, 18 mg/kg and 27 mg/kg. Part II: three doses will be investigated in Part II, the total daily dose of Ir-CPI will be determined based on the emerging safety, tolerability and pharmacokinetic data from Part 1.	NA
Route of Administration	IV infusion	IV infusion
Dosing instructions:	Refer to Section 7.3	Refer to Section 7.3
Packaging and Labelling	Study Treatment will be provided in boxes containing 30 x 10 R glass vials. Each box and vial will be labelled as required per country	

Study Treatment Name:	Ir-CPI	Placebo
	requirement.	
	Details of labelling are provided in Section 7.6.	
Manufacturer	Halix B.V.	Commercially available source

7.2. Method of Treatment Assignment

The randomisation list will be generated by an independent statistician, who will be different from the study statistician, using SAS® software. This list will be transmitted to the unblinded pharmacist of the clinical site in a secure way in order to maintain the blinding for the other staff members involved in this trial.

Two sets of individual sealed decoding envelopes will be also generated by the independent statistician: one set of the sealed decoding envelopes will be provided to the investigational site and one set will be provided to the pharmacovigilance contact for the trial.

For this double blind, placebo controlled, ascending dose trial of single dose infusions of Ir-CPI/Placebo, the participants will be randomised taking into account the specific requirements for the sentinel groups:

In Part 1:

Five (5) panels (A to E), each consisting of eight (8) healthy male participants will be randomised to receive either Ir-CPI or matching placebo: first, 2 sentinel participants (1:1 active / placebo) then for the rest of the group, a 5:1 ratio (active / placebo). The first four (4) panels will be administered Ir-CPI/Placebo in a sequential group design. Depending of the PK and PD results obtained for the first 4 panels, a fifth panel might be performed thereafter. In the end, this fifth panel was not performed.

In Part 2:

Three (3) panels F-G-H, each consisting of eight (8) healthy male participants will be randomized to receive either Ir-CPI or matching placebo: there will be 2 sentinel participants per group (one active treatment and one placebo), the rest of the group follows a 5:1 randomization ratio. The three (3) panels will be administered Ir-CPI/Placebo in a sequential group design. In the end, part 2 was not performed.

Table 4: Randomisation

Study Part	Group	Randomisation number	Replacement randomisation number	Randomisation ratio Active/Placebo
1	A	1101 to 1108	5101 to 5108	2 sentinels (1 active, 1 placebo) then for the rest of the group, 5:1 ratio
1	B	1201 to 1208	5201 to 5208	2 sentinels (1 active, 1 placebo) then for the rest of the group, 5:1 ratio
1	C	1301 to 1308	5301 to 5308	2 sentinels (1 active, 1 placebo) then for the rest of the group, 5:1 ratio
1	D	1401 to 1408	5401 to 5408	2 sentinels (1 active, 1 placebo) then for the rest of the group, 5:1 ratio
1	E	1501 to 1508	5501 to 5508	2 sentinels (1 active, 1 placebo) then for the rest of the group, 5:1 ratio
2	F	2101 to 2108	6101 to 6108	2 sentinels (1 active, 1 placebo) then for the rest of the group, 5:1 ratio
2	G	2201 to 2208	6201 to 6208	2 sentinels (1 active, 1 placebo) then for the rest of the group, 5:1 ratio
2	H	2301 to 2308	6301 to 6308	2 sentinels (1 active, 1 placebo) then for the rest of the group, 5:1 ratio

Participants withdrawn from the study retain their randomisation number, if already given. New participants must always be allotted a new randomisation number/treatment number (replacement treatment number): once assigned, randomisation numbers are never reused within the study site. Note that participants will be identified by their randomisation numbers, throughout the entire course of the study.

7.2.1. Blinding

The pharmacist and his/her attendant, the unblinded monitor who reviews the IMP-related documentation, and the bioanalytical staff (external lab) will be the only personnel to have access to the randomisation list in order to prepare the drug for administration. All Sponsor and Investigator site staff involved in the study will be blinded to the IMP assignment.

In order to maintain blinding, preparation of the dosing solution will be completed by the Good Distribution Practice (GDP) Pharmacy. All documents related to the Pharmacy should be kept in a locked and secure area in order to prevent any unblinding of the staff involved in the trial.

For participants who are randomised to active treatment, the solution of Ir-CPI supplied in vials at 25 mg/mL may be diluted in 0.9 % w/v sodium chloride to a final concentration calculated to achieve the correct dose according the participants weight and according dose assigned to the cohort.

Placebo treatment (0.9 % w/v sodium chloride) will be prepared. The GDP Pharmacy will prepare the IV infusions according to the randomization list and label them with a subject-specific label. Intravenous infusion of the IMP solution will be administered by the blinded study staff according to local SOPs. If needed, additional precautions (suitable ancillaries

such as coloured syringes and infusion lines) will be taken to ensure the blinding of the participant and Investigator.

Emergency code break procedure

In case of an emergency, when knowledge of the investigational product assignment is required for the medical management of an individual participant, the treatment for that participant may be unblinded. The Investigator must notify the Sponsor and study monitor within 24 hours after determining that it is necessary to unblind the treatment assignment for that participant only.

The Sponsor Medical Monitor should be consulted before unblinding, whenever possible.

This documentation must include the name of the individual breaking the blind, the date on which the blind was broken, and a description of the event that led to the unblinding. The Investigator must also indicate in source documents and in the eCRF that the blind was broken and provide the date, time, and reason for breaking the blind. Any adverse event (AE) or serious adverse event (SAE) associated with breaking the blind must be recorded and reported as specified in this protocol.

Unblinded monitors will routinely check the integrity of the envelopes that are stored at the site. All code envelopes (opened or not opened) will be collected from the site prior to study close-out and will be returned to the Sponsor.

7.3. Dose administration

The investigational products will be administered only to participants randomized in this study following the procedures set out in the present clinical study protocol.

The start and the stop time as well as the total volume of drug administered for each participant will be recorded.

7.3.1. IMP preparation

Ir-CPI will be supplied frozen, as a 5 mL PBS solution containing 25 mg/mL Ir-CPI in glass vials (10 mL) to be stored between -15°C and -25°C.

The total doses administered to the participants are presented in [Table 5](#) and [Table 6](#) for Part 1 and Part 2 respectively.

All doses are expressed in mg/kg, and the body weight of each participant at screening will be used to calculate the exact amount of study drug needed to prepare the allocated total dose for each participant.

The detailed instructions for preparing and calculating the doses of the IMP for administration are provided in the Pharmacy Manual.

7.3.2. Doses administered in Part 1

In Part 1, single doses of Ir-CPI or its matching placebo will be administered to the participants using a continuous 6-hour intravenous infusion.

Table 5: Part 1 Suggested Doses of Ir-CPI for Dose Escalation

Group	Infusion rate* (mg/kg/h)	Infusion Duration (h)	Ir-CPI target plasma concentration (µg/mL) at 6 hours	Total dose (mg/kg)
A	0.25	6	1.4	1.5
B	0.75	6	4.1	4.5
C	1.50	6	8.3	9
D	3.00	6	16.6	18
E**	4.5	6	24.8	27

*Weight of the participant at the screening visit will be used to calculate the dose of study drug.

***in the end, group E was not performed.*

7.3.3. Doses administered in Part 2

In the end, part 2 was not performed.

In Part 2, single doses of Ir-CPI or its matching placebo will be administered to the participants using a single ascending 30-minute loading dose infusion followed by a fixed dose of continuous 5.5-hour intravenous infusion

Table 6: Part 2 Suggested Doses of Ir-CPI for Dose Escalation

Group	Infusion rate** (mg/kg/h)	Time (h)	Ir-CPI target plasma concentration (µg/mL) between 30 min and 6 hours	Total dose (mg/kg)
F	Rapid infusion*: 6	0.5	8	11.25*
	Slow infusion*:1.5	5.5		
G	Rapid infusion*:7	0.5	8	11.75*
	Slow infusion*:1.5	5.5		
H	Rapid infusion*8	0.5	8	12.25*
	Slow infusion*:1.5	5.5		

* The rapid and the slow infusion rates will be calculated based on Part 1 emerging safety, PD and PK data. The total dose administered by rapid and by slow infusion will not exceed the highest total dose tested in Part 1. The infusion rate (in mg/kg/h) for the slow infusion will not exceed the maximum infusion rate used in Part 1. The dose may also be adjusted.

**Weight of the participant at the screening visit will be used to calculate the dose of study drug

7.3.4. Dosing and meals

Dosing is described in Section 5.1. Meals and food intake are described in Section 6.3.

7.4. Dose Escalation Rules and Dose Staggering Approach

Given the new mechanism of action, the nature of the compound (peptide) and the intended route of administration, dose staggering will be applied in this FIH trial for all panels. This dose staggering will be as such that 2 participants will be dosed at least 24 hours before the remainder of the cohort. These 2 sentinel participants will be randomised as such that there will be one placebo and one *verum*, as shown in Table 4. After the review of adverse events, vital signs, safety labs and ECGs collected over 24 hours postdose (D2), the remaining participants of the cohort will receive the same dose level. Following completion of the initial 24-hour safety period for the sentinel participants, the decision to proceed with the remaining participants in that cohort will be mutually discussed/agreed upon between Investigator (or his designee) and the Sponsor and the decision to dose will be formally confirmed by the

Sponsor. The proposed minimal 24 hours between the sentinel and the remainder of the cohort is deemed sufficient because this is a single intravenous infusion where it is expected that the most severe and acute reactions will occur during or very short after the infusion. Based on animal data, the pharmacodynamic effect and potential side effects are expected to be related to plasma levels that will decline rapidly after ending the IV infusion.

At each dose level, after completion of Investigational Medicinal Product (IMP) administration in at least 6 participants (i.e. a minimum of 4 on active treatment), the Investigator will provide a comprehensive Investigator Safety Report which will include (but not limited to) the following content:

- Relevant information on participants' demographics/characteristics, medical history, physical examination, concomitant medications;
- List of all AEs, including severity, time of onset related to study drug administration, duration, clearly highlighting AESI and Serious Adverse Events (SAEs) and relatedness/causality of AEs;
- Any clinically significant out of ranges safety clinical laboratory tests results (as assessed by the PI);
- Physical Examination (including basic neurological testing for isocoria, light reflexes, gait and balance) results including clinical significance for abnormal findings;
- ECG and Vital Sign results including clinical significance for abnormal values;
- Statement of the Principal Investigator's recommendation regarding dose decision.

Escalation to the next higher dose will only take place after review of the Investigator Safety Report from the previous dose levels by the Investigator, in consultation with the Sponsor's representative [called hereafter the Safety Review Committee (SRC)]. Dose escalation will be based on emerging safety and tolerability data as defined by adverse events, laboratory results, ECGs, vital signs, and telemetry assessments. Other parameters of interest will be assessed (blinded pharmacokinetics, blinded pharmacodynamics) per SRC charter and section 7.5 criterion n°5, before dosing in the next cohort can start.

Within the planned dose range, a dose lower than the next planned dose may be tested, depending on emerging safety, tolerability and/or other relevant data, such as blinded pharmacokinetics or pharmacodynamics. The final dose to be used for each cohort will be decided based on the results of the previous panel and can be adjusted downward if deemed necessary.

If the highest planned dose level is found to be safe and tolerable, also considering the PK and PD data, additional higher doses may be added by amendment.

Between the first patients (sentinels) of two consecutive panels, a period of at least 7 days will be respected.

7.5. Stopping Rules

The SRC will meet for deciding on the continuation of dosing after drug administration in at least 6 participants [i.e. a minimum of four (4) on active treatment]. However, stopping rules will be applicable from dosing of the first sentinel participant on. These decisions will be based on the following:

1. If a Serious AE, which is considered drug-related, occurred in one (1) participant or if a Severe AE, which is considered drug-related, occurred in two (2) participants in the same cohort, the dosing in the trial should be temporarily stopped in order to review additional

safety data. If after review of the additional data and unblinding of the randomisation for that participant the drug-relatedness assessment changes, the study can resume without substantial amendment.

2. If 1 sentinel participant (out of 2) or at least two (2) out of eight (8) participants in a cohort experience a Dose Limiting Toxicity (DLT) that is related to Ir-CPI administration, the dosing in the trial should be temporarily stopped in order to review additional safety data. If after review of the additional data and the unblinding of the randomisation for that participant, the drug-relatedness assessment changes, the study can resume without substantial amendment;
3. If at least one (1) DLT is reported, the SRC recommendation will depend on the DLT profile (i.e. identical DLTs in different participants) or the frequency and severity of DLTs in the same participant and on the recommendation made by the Investigator;
4. If no DLT is reported, the planned dose escalation may proceed with the next cohort or part, unless the Investigator has any other safety concern;
5. In any case, administered dose of Ir-CPI will be limited to a dose predicted to generate upper 95 % confidence interval (CI) C_{max} value being not higher than the lowest C_{max} values at the NOAEL (53.7 $\mu\text{g/mL}$) in the most sensitive species [24h-infusion acute study in monkeys at NOAEL 201.6 mg/kg/day]. PK data will be monitored, so that preliminary PK parameters of the 1.5 mg/kg panel (A) should be available before dosing the 4.5 mg/kg panel (B), 4.5 mg/kg panel (B) PK parameters before administration of 9 mg/kg panel (C) etc.

All decisions will be documented in writing and communicated to the study team in a timely manner, before dosing in the next cohort can start.

Definition of the DLT:

- Serious AE drug-related in one (1) participant (in the study);
- Severe AE drug-related in two (2) participants in one cohort;
- ECG: prolongation of QTcF to >500 ms or of >60 ms over baseline drug-related in two (2) participants in one cohort;
- Safety laboratory tests: Increase in ALT/AST ≥ 5 x ULN in 2 participants in the study;
- Safety laboratory tests: Increase in ALT/AST ≥ 3 x ULN and TBIL ≥ 2 x ULN in one (1) participant in the study;
- Other clinically significant changes in safety clinical laboratory tests, ECG, VS or other safety parameters deemed as a significant safety concern by the Investigator;
- aPTT increase > 5 x ULN at the 24h postdose time point in two (2) participants in one cohort;
- Hypersensitivity reaction occurring during study drug administration or within 6h after end of study drug administration accompanied by symptomatic bronchospasm, with or without urticaria; allergy-related oedema/angioedema; hypotension in one participant.

If no further dosing is planned due to the stopping criteria as described above, previous randomised and dosed participants will continue the study as planned. Safety assessments will be performed as planned. Pharmacokinetic assessments will be performed if deemed to be relevant and agreed by the Investigator and Sponsor without compromising the safety of a participant.

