
Within the planned dose range, a dose lower than the next planned dose may be tested, depending on emerging safety, tolerability and/or other relevant data, such as blinded PK or PD. The final dose to be used for each cohort will be decided based on the results of the previous panel and can be adjusted downward if deemed necessary. If the highest planned dose level is found to be safe and tolerable, also considering the PK and PD data, additional higher doses may be added by amendment.
 
Within each panel, the first 2 study participants will be designated as sentinel study participants. The sentinel study participants will be randomized 1:1 to receive either placebo or Ir-CPI (1 study participant each). Between the first participants of 2 consecutive panels, a period of at least 7 days will be respected between the administrations of treatment.
 
The PI and Sponsor medical monitor will review at least 24hrs of post-dose safety data (vital signs, labs, electrocardiograms [ECGs], telemetry and physical examination) for the sentinel study participants. If no safety concerns are identified, the remainder of the cohort will be randomized in a 5:1 ratio and dosed.
 
The SRC will meet for deciding on the continuation of dosing after intake in at least 6 participants (i.e. a minimum of 4 on active treatment). However, stopping rules will be applicable from dosing of the first sentinel participant.

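### The one-sentinel stopping clause cannot act through the aPTT or QTcF dose-limiting toxicity, nor through the study's first ALT/AST case, because those items already require two participants

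*Protocol*

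**What the plan says.** Protocol 7.5 states that the "stopping rules will be applicable from dosing of the first sentinel participant on". Rule 2 is triggered as follows: "If 1 sentinel participant (out of 2) or at least two (2) out of eight (8) participants in a cohort" have a DLT related to Ir-CPI. Dosing then stops temporarily for a safety review.

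The DLT list that follows has eight items. Four carry a count of two participants:

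- severe drug-related AE, two in one cohort;
- "ECG: prolongation of QTcF to >500 ms or of >60 ms over baseline drug-related in two (2) participants in one cohort";
- ALT/AST of at least 5 x ULN, two in the study;
- "aPTT increase > 5 x ULN at the 24h postdose time point in two (2) participants in one cohort".

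Three apply to a single participant: a drug-related SAE, ALT/AST of at least 3 x ULN with bilirubin of at least 2 x ULN, and a hypersensitivity reaction. One has no count: "Other clinically significant changes in safety clinical laboratory tests, ECG, VS or other safety parameters deemed as a significant safety concern by the Investigator".

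On the sentinels, Protocol 7.4 says "These 2 sentinel participants will be randomised as such that there will be one placebo and one" active. After 24 hours of sentinel data, "the decision to proceed with the remaining participants in that cohort will be mutually discussed/agreed upon between Investigator" and Sponsor, with formal confirmation by the Sponsor. The Synopsis adds: "If no safety concerns are identified, the remainder of the cohort will be randomized in a 5:1 ratio and dosed".

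**The concern.** The count is applied twice. Rule 2 already says how many participants must have a DLT: one sentinel, or two of eight. When the DLT definition itself needs two participants, the one-sentinel half of rule 2 has nothing to act on.

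This matters most for aPTT, which the protocol treats as its marker of drug activity (3.3 and 5.6). An active sentinel above 5 x ULN at 24 hours, or with QTcF above 500 ms, is not a DLT under the numeric item written for that finding. Rule 3, which needs at least one reported DLT, is then not engaged by that item either. Release of six more participants, five of them on the same dose, rests on judgement. Because the aPTT item is read at 24 hours and 7.4 sets no interval among the remaining six, all six could be dosed before a second 24-hour value exists.

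**Working it through.** **Inputs from the documents.** A panel has 8 participants, 6 active and 2 placebo (Protocol 5.2.1). The sentinel pair is 1 active and 1 placebo; the other six are 5 active and 1 placebo (5.1.1, 7.2). Check: 1 + 5 = 6 active and 1 + 1 = 2 placebo. The plan gives no operating characteristics for the stopping rules and no event rates (10.2.1 says the sample size is not based on power), so there is no figure to reproduce.

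**Step 1: sentinel stage as written.** The aPTT or QTcF item needs 2 participants in the cohort. Active sentinels = 1, and 1 < 2. The probability that the active sentinel alone meets either item is 0 for every event rate p, including p = 1. On a literal blinded reading, both sentinels could show the finding. With an assumed placebo rate of 0 to 5%, that has probability at most 1 x 0.05 = 5% even at p = 1, and the placebo participant's finding could not be related to Ir-CPI.

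**Step 2: the other counted items.** The ALT/AST item counts across the study. A sentinel who is the study's first case cannot meet it; once an earlier case exists, a sentinel can. The severe-AE item has the same structure, but it matches rule 1, which also requires two severe related AEs in one cohort.

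**Step 3: cost of defining one item per participant.** Assumptions: p is the event rate per active participant, the placebo rate is 0, participants are independent, and every case is judged related.

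- Pause as written: P(at least 2 of 6) = 1 − B(p), where B(x) = (1−x)^6 + 6x(1−x)^5.
- Pause after the change: sentinel positive, or at least 2 of 6.
- Difference: the sentinel is the only case, p(1−p)^5.

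| p | as written | after change | difference |
|---|---|---|---|
| 0.02 | 0.6% | 2.4% | 1.8% |
| 0.05 | 3.3% | 7.1% | 3.9% |
| 0.10 | 11.4% | 17.3% | 5.9% |
| 0.30 | 58.0% | 63.0% | 5.0% |

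The maximum is at p = 1/6: (1/6)(5/6)^5 = 6.7%.

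**Step 4: cost of changing aPTT and QTcF together.** Let the rates be a and q, independent, and p = 1 − (1−a)(1−q). No pause as written has probability B(a)B(q). No pause after the change has probability (1−p)^6 + 5p(1−p)^5. The difference is the extra pause rate.

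- a = q = 0.02: p = 0.0396; 0.9887 − 0.9465 = 4.2%.
- a = q = 0.05: p = 0.0975; 0.9355 − 0.8322 = 10.3%.
- Maximum over all a and q: 18.8%, near a = q = 0.14.

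**Step 5: ALT/AST.** With rate r, adding a sentinel clause creates a new pause only if there is no earlier case in the study and the sentinel is the sole case in the cohort. That is at most r(1−r)^5, so 1.8% at an assumed r = 0.02.

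**Step 6: the aPTT threshold.** Protocol 5.6 gives a generally accepted therapeutic range of 150% to 250% of ULN. The DLT limit is 5 / 2.5 = 2 times the top of that range.

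**The case against.** **Judgement routes remain.** The uncounted DLT item names safety laboratory tests and ECG. The Investigator can declare a single sentinel's aPTT or QTcF a DLT under it, and rule 2 then fires. The default after the sentinels is also to hold: the other six are dosed only if no safety concern is found and the Sponsor formally confirms. Safety aPTT is a listed blood safety parameter (9.7.6.2.1) and is readily available to the Investigator (5.6). All of this stands. A reader might infer that a sentinel with an extreme aPTT could not stop dosing, and the documents do not support that. These routes do not restore a numeric trigger fixed in advance.

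**The trigger would not be automatic anyway.** Rule 2 requires the DLT to be related to Ir-CPI, and the QTcF item repeats that condition. This stands: the corrected rule would fix the threshold, not remove judgement.

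**Single-participant aPTT is handled elsewhere.** From Cohort D, one participant above twice baseline at 24 hours keeps all participants in hospital to 48 hours and adds a 36-hour sample (5.1.1). True, but that rule governs discharge, not dosing. It also shows that one participant's value is treated as actionable at a far lower level.

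**The count of two may be deliberate.** aPTT prolongation is the intended pharmacology, and the range in 5.6 is a general one, so it cannot prove that intended activity stays below 5 x ULN. That caution is fair. But a deliberate count of two would leave the sentinel clause without effect for these items, and rule 2 already supplies two of eight for non-sentinels.

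**Little is left to change.** Part 1 ended at Cohort D and Part 2 was not run. This stands and limits the practical reach.

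**Conclusion.** The inconsistency is real and follows from the wording alone. The one-sentinel clause has probability 0 of acting through the aPTT or QTcF item, and cannot act through ALT/AST of at least 5 x ULN for the study's first case. Four of the eight DLT items carry a two-participant count; the severe-AE item is consistent with rule 1 and need not change. The loss is the prespecified numeric sentinel trigger.

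The documents do not show that protection was absent or that any participant was dosed unsafely, and they give no event rate from which harm could be estimated. The zero in Step 1 needs only the one-active sentinel pair and a rule 2 confined to events related to Ir-CPI. The pause rates in Steps 3 to 5 rest on assumed rates, independence, no placebo events and every case being judged related. The point bears only on panels added by amendment, which Protocol 5.2 and 7.4 allow.

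**What to change.** In Protocol 7.5:

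- Delete the closing requirement for two participants in one cohort from the aPTT and QTcF items, so that each applies per participant and rule 2 does the counting.
- Keep the study-wide count of two for ALT/AST of at least 5 x ULN, and add *or in one sentinel participant*.
- Leave the severe-AE item aligned with rule 1.

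A minor tidy-up: the sentinel review lists differ (3.3 omits laboratory tests; 7.4 and the Synopsis include them). Use one list and name the 24-hour safety aPTT in it.

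The cost is a few phrases and no new samples. The price in conduct is an occasional extra temporary pause, after a single sentinel case or after two different single-participant DLTs in one cohort, at the rates given above. Under rule 2, dosing can resume without a substantial amendment if review and unblinding change the relatedness assessment.
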